#### Phase 3: Pilot RCT (Yr. 4)

**Overview.** Forty parents of young children will be randomized to intervention (i.e., initial check-up [level 1]) or control conditions (i.e., assessment only), with follow-up assessments at 1-month and 3-months.

**Participants and Procedures.** Parent recruitment methods will be identical to those described in Phase 2. A second assistant (i.e., a research technician) will be hired at the beginning of this year in order to make recruitment feasible. Participating parents will be compensated \$25 for baseline participation, \$25 for completing the 1-month follow-up, and \$50 for completing the one-month follow-up.

**Randomization.** Randomization will be automatically generated by CIAS. Parents randomized to the control condition will only complete the evaluation measures (see Table 1) and select goals. Parents randomized to the intervention condition will complete the full initial check-up (Level 1; see Figure 3b). All parents (both

control and intervention) will be given a brochure to access the PT website by the research assistant; including unique login number that will allow us to examine if completing the full initial check-up impacts website use.

**Follow-up.** We will follow up with participants in both conditions by sending links to online surveys at one month and three months after baseline (these questionnaires will be done through Qualitrics; see www.qualtrics.com). Parents will complete all evaluation measures (Table 1) at each time point. We will communicate by phone and by regular email with participants who do not complete the survey in an attempt to prompt participation or establish that the participant is choosing to stop their participation.

Measures. Table 1 outlines measures used for evaluation, the construct each measure taps into, and assessment points for each measure. The primary outcome of interestuse of the PT website-will be measured via rates of visiting the website for each assigned user ID (gathered via using Google Analytics). The secondary outcome of focus, items consistent with the TPB, will be measured with items made specifically for this project; rated on a 5-point scale with 3 items tapping into each domain. Internal consistency will be examined for the measure as a whole and item domains. As mentioned previously, the ECBI will be used to screen children for disruptive behavior problems. The ECBI taps into parents' perceptions of child disruptive behavior through 36-items in which caregivers rate the frequency of specific challenging child

Table 1: Evaluation N	Measures			
Construct	Measure name (author)		Assessment P	oint
	· ,	BL	1-month	3-month
Disruptive behavior problems	Eyberg Child Behavior Inventory (ECBI; Eyberg & Pincus, 1999; Intensity and Problem scales)	х	х	х
Parenting practices	Alabama Parenting Questionnaire—Preschool Revision (Clerkin, Marks, Policaro, & Halperin, 2007)	x	Х	x
		X	X	X
Parents' Theory of Planned Behavior (TPB)	Items made specifically for this project with three items tapping into each domain of TPB			
Use of Parenting Training Website	Tracking of username logins through Google analytics tool		х	X
Technology Acceptance Questionnaire (intervention group)	Items made for this project tapping into ease of use, usefulness, and overall satisfaction	х	х	х

behavior (e.g., "does not obey") on a 7-point Likert scale (ranging from 1 = Never to 7 = Always) and also if the behavior is perceived as a problem for the parent (rated as "yes" or "no). The ECBI will be re-administered at follow-up. The Alabama Parenting Questionnaire—Preschool Revision (Clerkin, Marks, Policaro, & Halperin, 2007) will be incorporated in the initial check-up, and will be re-assessed at each follow-up. The APQ-PR stems from the widely used Alabama Parenting Questionnaire (Frick, Christian, & Wooton, 1999) and has parents rate how typical specific parenting behaviors occur (e.g., "You let your child know when he/she is doing a good job with something") on a 5-point scale (ranging from 1=Never to 5=Always). For the intervention group, intervention acceptance will be measured through a brief questionnaire made for this project. All measures are purposefully brief and the number limited to increase feasibility.

Data Analyses. Data analyses will use an intent-to-treat approach using multiple imputation for participants lost to follow-up. Primary Hypothesis:: The intervention group (i.e. those randomized to complete the full initial check-up [level 1]; n = 20) will visit the PT website more often than the control group (i.e., assessment only; n = 20). Secondary Hypothesis (a):: Participants assigned to the intervention group, as compared to those in the control group, will have higher scores for all domains consistent with the TPB at follow-up. For both primary and secondary (a) hypotheses, we will examine descriptive analyses and conduct ANCOVA, t-test analyses, and effect size calculation (Cohen's d) to determine group differences. Low power may inhibit finding statistically significant results. Secondary Hypothesis (b). Participants in the intervention group will report high levels of satisfaction (>=4 on a 5-point scale); examined through descriptive statistics. Exploratory analyses: We will also explore if randomization to the intervention group and actual use of the PT website leads to fewer disruptive behaviors and improved parenting practices at follow-up. ANCOVAS, t-tests, and effect size (Cohen's d) calculation will be used for these exploratory analyses.

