Technical aspects of program creation. The initial check-up will be programmed using the Computerized Intervention Authoring System (CIAS), a web-based authoring tool that allows the creation of highly interactive brief interventions without the need for programming. Consistent with the Elaboration Likelihood Model (Petty & Cacioppo, 1986), which posits that tailoring health content to the individual increases perceived relevance, system logic within CIAS enables branching and tailoring. That is, content is presented in a customized manner, dependent on prior responses. Interventions created through CIAS have been successfully used by parents in multiple previous randomized trials, and these parents have given high ratings for ease of use (e.g., [name] et al., 2014). The most recent version of CIAS deploys as a cross-platform compatible mobile web app, making it accessible on any mobile device, and is also able to send tailored emails and text messages.

The level 2 PT website will be created using Wix.com. Wix is a user-friendly platform allowing individuals without programming experience to create sophisticated HTML5 websites that use responsive web design, making them compatible with mobile devices of all types and sizes. The website will be created by the PI and project RA. Given how important ease of use is, a Wix programming consultant will be hired in year 1 in order to generate suggestions for improvements. The website will be username protected. Wix websites are highly flexible and scalable, and also allow for implementation of custom coding if necessary.

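### Could the Phase 3 multiple-imputation rule overwrite website use that the login record has already captured?

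*Combined protocol and SAP*

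**What the plan says.** The relevant text is in Phase 3: Pilot RCT, with one supporting line under Proposed intervention.

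- **Size.** "Forty parents of young children will be randomized to intervention" or to an assessment-only control. The Data Analyses paragraph gives the arms as "those randomized to complete the full initial check-up [level 1]; n = 20" and "control group (i.e., assessment only; n = 20".
- **Primary outcome.** Under Measures, use of the parent training website "will be measured via rates of visiting the website for each assigned user ID (gathered via using Google Analytics". Table 1 lists it as username login tracking at 1 and 3 months.
- **Who is tracked.** Under Randomization, parents in both arms receive a brochure "including unique login number that will allow us to examine if completing the full initial check-up impacts website use". The technical description of the site adds: "The website will be username protected".
- **Follow-up.** This consists of online surveys at 1 and 3 months. For non-response: "We will communicate by phone and by regular email with participants who do not complete the survey".
- **Missing data.** "Data analyses will use an intent-to-treat approach using multiple imputation for participants lost to follow-up". This is the only missing-data rule. It names no outcome, and the plan does not define loss to follow-up.

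**The concern.** The imputation sentence is framed by participant, not by missing value, and the primary hypothesis comes directly after it. Elsewhere in Phase 3, follow-up means surveys, so a parent lost to follow-up would most naturally be one who stops returning them. The primary outcome does not need a survey: the login record goes on accumulating. A literal reader could therefore blank a non-responder's whole follow-up row, including visits already on record, and impute it.

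That would matter. The pilot has 20 parents per arm, and the plan itself warns of low power. Replacing recorded counts would cost precision. It could also shift the group difference if parents who never visit the site are also less likely to answer surveys about it. The Summary and Future Directions section says the next grant application will rest particularly on data about use and impact, so the primary outcome is the one most worth protecting.

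**Working it through.** The plan gives no figure to reproduce: Phase 3 states no power, effect size, visit rate or dropout rate. The arm sizes agree with the total (20 + 20 = 40). The check is mainly a reading of the text, with a short calculation for scale.

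**Step 1. Which follow-up values depend on a survey?**

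| Follow-up measure (Table 1) | Source | Lost if the survey is not returned? |
|---|---|---|
| Website use (primary) | Login tracking by assigned ID | No |
| Theory of Planned Behavior items | Online survey | Yes |
| Child behaviour inventory, parenting questionnaire | Online survey | Yes |
| Technology acceptance (intervention arm) | Parent questionnaire | Yes |

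Survey non-response empties the last three rows and leaves the first filled.

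**Step 2. What does the rule do to each row?** Multiple imputation draws values for cells that are empty. Applied to this table, it acts on the survey measures and leaves website use alone. Survey loss then causes 0 of 40 primary-outcome values to be imputed, whatever the loss rate.

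**Step 3. Is an unused login a zero or a missing value?** The outcome is a visit rate for each *assigned* ID, so the denominator is the list of IDs handed out, not the list of IDs that appear in the analytics export. A working ID with no recorded login has zero visits. The primary hypothesis asks which arm visits more often, and it cannot be tested sensibly if non-visitors are treated as unknown.

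**Step 4. What would the other reading cost?** Every rate here is assumed, because the documents give none. If a share L of parents is lost to the surveys and their recorded use is discarded, 40(1 − L) values are kept and 40L replaced:

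- L = 10%: 36 kept, 4 replaced.
- L = 20%: 32 kept, 8 replaced.
- L = 30%: 28 kept, 12 replaced.

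*Precision.* If loss is unrelated to use and imputation has no auxiliary information, the standard error grows by 1/√(1 − L). At L = 20% this is 1/√0.80 = 1.118, about 12%. Power at two-sided 0.05 is roughly Φ(d√(n/2) − 1.96), with n parents per arm. For an assumed d = 0.8:

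- n = 20: Φ(2.530 − 1.96) = 72%.
- n = 16: Φ(2.263 − 1.96) = 62%.

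*Bias.* Let p be the true share who ever visit, and let Lu and Ln be the loss rates in users and non-users. Imputing from responders in the same arm gives an expected share of p(1 − Lu) / [p(1 − Lu) + (1 − p)(1 − Ln)]. Take true shares of 20% (control) and 40% (intervention), a difference of 20 points:

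- Lu = Ln = 20%: the shares stay at 20% and 40%, with no bias.
- Lu = 10%, Ln = 30%: 0.18/0.74 = 24.3% and 0.36/0.78 = 46.2%, a difference of 21.8 points.
- Lu = 10%, Ln = 50%: 0.18/0.58 = 31.0% and 0.36/0.66 = 54.5%, a difference of 23.5 points.

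**Step 5. Which reading does the text support?** The imputation sentence opens with intent-to-treat, which points to using the data held on everyone randomised. The Randomization paragraph says logins go to both arms so that the effect on use can be examined. No sentence tells the analyst to set recorded logins aside. The costs in Step 4 therefore attach to a reading that the plan does not ask for.

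**The case for a change.** The best case for a change has two parts.

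First, the plan itself groups login data with survey data. Table 1 places website use at the same 1- and 3-month points as the questionnaires, and the Follow-up paragraph says parents complete all the Table 1 measures at each time point. An analyst working from a visit-based dataset might flag the whole visit as missing. This is fair as a description of loose drafting: the scope of the imputation rule is unstated. But parents do not complete login tracking, and Table 1 names its source. To impute over it, an analyst would have to delete primary-outcome data already in hand. That takes an active error, not just a gap in the text.

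Second, the handling of an ID with no login is not written down, and such IDs may be common. The silence is real, but defining the outcome per assigned ID leads to zero as the natural entry.

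There is also a point in favour of leaving the rule general. The Follow-up paragraph foresees parents who choose to stop taking part, and tracking could fail for an ID. Use data might then be truly unavailable, and imputation could be legitimate. A blanket statement that website use is never imputed and always scored zero when absent would handle those parents badly. It is not the costless tightening that it seems.

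**Conclusion.** The observation is accurate: the imputation sentence does not say that it is confined to values that are actually missing. It does not amount to a flaw that needs correcting. Under the ordinary meaning of multiple imputation, recorded website use enters the analysis for every randomised parent and the effect on the primary result is zero.

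The power loss and bias shown above need an analyst to discard recorded data, and they rest on loss and visit rates that the documents do not supply. They show what an unlikely mistake would cost, not what the plan is expected to cost. The conclusion assumes that per-ID tracking works as described. Where it fails, or a parent's data cannot be used after withdrawal, the existing rule already gives a reasonable route.

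The point concerns Phase 3 only. The cover letter states that the posted investigation is Phase 2, a non-randomised trial with 6 participants, so no reported result is affected.

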## Theoretical models

[figure not shown]
Two theoretical models will guide intervention development and evaluation. First, the technology acceptance model (TAM; Davis, 1989) suggests use of new technology is highest when users perceive it as easy to use (i.e., requiring low effort) and useful (i.e., use will positively impact the users' performance). Design of the system will center on creating a system that is perceived as easy to use and useful. Second, the Theory of Planned Behavior

(TPB; Ajzen, 1991) suggests that key beliefs, including attitudes, subjective norms, and perceived control, motivate behavior through their effect on change intentions. As depicted in Figure 1, mechanisms linking completion of the initial check-up (level 1) with use of the PT website (level 2) may be consistent with the TPB. That is, the initial check-up (level 1) will motivate use of the PT website (level 2) by altering parents' attitudes towards children's behavior, perceptions of child behavior norms, and perceived control over child behavior.

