#### **Proposed intervention**

Although page limits prohibit an exhaustive description of the intervention, Figure 2 provides an overview of key proposed PYCC processes and content. As previously mentioned, there will be two main parts to the intervention: An initial check-up completed on a tablet at a healthcare visit (level 1), and a PT website that aims to teach specific skills that are common elements of behavioral PT programs (level 2; reviewed interventions

include Parent-Child Interaction Therapy [Zisser & Eyberg, 2010], The Incredible Years [Webster-Stratton et al., 2013], Brief Behavioral Intervention [Axelrad, Butler, Dempsey, & Chapman, 2013], Parent Management Training [Patterson, Reid, & Dishion, 1992], and Triple P [Sanders, Bor, & Morawska, 2007]). Both levels will incorporate an animated narrator and high quality, professionally made videos featuring professional actors (further information below). While parents will be encouraged to access all content on the PT website, parents will have input regarding how they move through the content and, ultimately, what content they use (creating a tailored intervention); this is similar to the tailoring done in the evidence-based Family Check-up (Gill, Hyde, Shaw, Dishion, & Wilson, 2008) as families choose the number and focus of intervention sessions. This choice will be made by parents as part of the initial check-up (see Figure 2b). The two intervention levels will be connected through text and email messaging (see Figure 2c for an example), which will prompt parents to complete sessions. Importantly, intervention creation will be highly influenced by all aspects of the training plan—allowing the candidate to transform gained knowledge into hands-on experiences creating a motivational mHealth intervention (training goal 1), carrying out qualitative data collection (training goal 2), and incorporating the PYCC into the work flow of a health care visit (training goal 3). Further, following the ORBIT framework, specific content will be influenced by data collected during the "Define & Refine" stage (see Figure 3. Step 2). Input from parents and professionals will guide specific decisions about presentation of materials. frequency of contact (e.g., frequency of messages), and presentation of content, in order to maximize technology acceptance.

1tailored based on screening results (e.g., severity of DBP; current motivation to change); 2tailored based on goals

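### Minor, Phase 3 only: one exploratory sentence puts randomised arm and self-chosen website use under the same causal verb, and intent-to-treat protects only the comparison by arm

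*Combined protocol and SAP*

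**What the plan says.** All references are to the combined protocol and SAP.

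- **Phase 3, Data Analyses, opening statement:** "Data analyses will use an intent-to-treat approach using multiple imputation for participants lost to follow-up".
- **Same paragraph, exploratory analyses:** the team will explore whether "randomization to the intervention group and actual use of the PT website leads to fewer disruptive behaviors and improved parenting practices". The methods follow: "ANCOVAS, t-tests, and effect size (Cohen's d) calculation will be used for these exploratory analyses". No covariates are named, no grouping by use is defined, and nothing says that use is not randomised.
- **Phase 3, Overview and Randomization:** forty parents are randomised, 20 per arm, to the initial check-up or to assessment only. Of all parents it is said: "control and intervention) will be given a brochure to access the PT website by the research assistant".
- **Phase 3, Measures:** website use is the primary outcome, counted as "rates of visiting the website for each assigned user ID". The ECBI is described as capturing parents' "perceptions of child disruptive behavior through 36-items".
- **Theoretical models:** the Theory of Planned Behavior (TPB) is adopted, in which "key beliefs, including attitudes, subjective norms, and perceived control, motivate behavior through their effect on change intentions". The check-up is expected to raise website use through these beliefs.

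**The concern.** The sentence holds two questions. Whether being randomised to the check-up improves child behaviour and parenting is answered by the randomisation. Whether using the website improves them is not, because parents decide for themselves whether to visit. The two share one causal verb and one list of methods.

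If the plan is followed as written, a t-test or Cohen's d by website use could be reported as an effect of the site when it partly or wholly reflects which parents chose to visit. The Summary and Future Directions section says that data on use and impact will inform the R01 application, so such a figure could be carried forward.

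**Working it through.** There is no figure in the plan to reproduce, so the check is first one of logic and then an illustration of size.

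**Step 1: what randomisation covers.** Arm is assigned by the CIAS software. Use is not assigned. It occurs after randomisation, can occur in either arm because both receive the brochure and login, and is itself an outcome. Intent-to-treat keeps parents in their assigned arm. Multiple imputation fills in lost outcomes. Neither balances users against non-users.

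**Step 2: is a common cause plausible from the documents?** Yes. The plan's own theory says that attitudes, norms and perceived control drive behaviour, including website use. The ECBI records what parents perceive. The same beliefs could affect both. This makes confounding plausible; it does not show that it is present.

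**Step 3: which contrast by use?** The text allows at least four: users against non-users, intervention-arm users against controls, visit rate as a continuous exposure, or a pathway from check-up through use to outcome.

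**Step 4: illustrative size. Every input except 20 per arm is an assumption.** Null trials were simulated with no effect of arm or website, a two-sided 5% level and a baseline-to-follow-up correlation of 0.6. There were 5,000 to 6,000 trials per setting. A parent is a user when a propensity Z passes a threshold. Motivation M correlates r with Z, and is linked to the outcome in one of three ways:
- A: r with follow-up only, baseline independent of M
- B: r with both baseline and follow-up
- C: r with the part of follow-up that baseline does not explain

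Analytic check for users against non-users at 50% use. The gap in mean Z is 2 × √(2/π) = 1.596, and under A and B the correlation of Z with outcome is r².
- r = 0.3: 1.596 × 0.09 = 0.14 SD
- r = 0.5: 1.596 × 0.25 = 0.40 SD

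False positives at r = 0.5 with 50% use in each arm:

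| Analysis | A | B | C |
|---|---|---|---|
| Users vs non-users, t-test | 23% | 24% | 16% |
| Users vs non-users, adjusted for arm and baseline outcome | 33% | 9% | 23% |
| Visit rate, adjusted for arm and baseline outcome | 48% | 11% | 32% |
| Intervention-arm users vs controls | 7% | 8% | 7% |
| By arm, ANCOVA | 5% | 5% | 5% |

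Other settings:
- Over all three models, with use of 50%/50% or 75%/25% by arm, the users vs non-users t-test gave a spurious difference of 0.09–0.15 SD and 6–8% false positives at r = 0.3, and 0.25–0.40 SD and 12–24% at r = 0.5.
- Intervention-arm users vs controls gave 5–6% at r = 0.3 and 5–8% at r = 0.5.
- Pathway reading at 75%/25% use: spurious indirect effect of 0.03–0.07 SD at r = 0.3 and 0.09–0.21 SD at r = 0.5.
- At r = 0 all tests gave 4–6%. Reversing the link with use reverses the sign of the bias.
- A different assumption set (motivation–use correlation 0.6, use of 20%/50% or 30%/60% in control/intervention) gave 12–13% for users vs non-users at a motivation–outcome correlation of 0.3 and 26–28% at 0.5. The comparison by arm stayed at 4.7–5.5%.

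**Step 5: precision of the comparison by arm.** The unadjusted 95% half-width is 1.96 × √(2/20) = 0.62 SD. With ANCOVA and a baseline correlation of 0.6 it is 2.026 × √(2/20) × √(1 − 0.36) = 0.51 SD.

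**The case against.** The strongest reply is that this is one sentence, labelled exploratory and phrased as something to explore, in a pilot that already admits low power. The cover letter says that the posted study is Phase 2, a non-randomised study with six participants and no hypothesis. That stands, and it caps the point at minor.

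It can also be said that the faulty analysis is inferred. This stands in part. A reader might infer that the plan will set aside the randomised comparison in favour of users against non-users. The documents do not say so: the intent-to-treat statement opens the paragraph, and the sentence is ambiguous. On one reading, intervention-arm users against controls, the simulated error rates are close to nominal.

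The sizes are not evidence about this trial. The documents give no use rate, correlation or SD, and changing the assumptions moves the results appreciably.

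The remark under Proposed intervention that "parents will have input regarding how they move through the content and, ultimately, what content they use" is only partial support, since it concerns tailoring of content rather than whether a parent visits. The case that use is voluntary rests mainly on the brochure design and on use being the primary outcome.

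None of this removes the problem that the wording offers a causal reading of a non-randomised exposure.

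**Conclusion.** The point holds as a minor matter of wording and specification in Phase 3. Intent-to-treat protects the comparison by arm and cannot protect a contrast by use, whichever contrast is meant. The primary hypothesis and secondary hypothesis (a) compare arms and are unaffected.

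The size of any bias is unknown, could be zero, and could go either way. Two stronger inferences are not supported. One is that the use result would necessarily flatter the website; nothing in the documents fixes the direction. The other is that, because both arms get the site, the comparison by arm excludes the website. The plan expects the check-up to raise website use, so that comparison is a total effect that includes whatever is carried by extra use. It does not isolate the effect of the website.

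**What to change.** Split the sentence in two.

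1. **By arm.** Compare ECBI and APQ-PR between randomised arms in all 40 parents, by ANCOVA on the baseline value with a 95% CI. Describe the result as the total effect of being offered the check-up, including any effect through extra website use.
2. **By use.** Report website use against outcomes separately, worded as an association. Use regression adjusted for arm, baseline outcome and the baseline TPB items. Table 1 appears to collect these at baseline (the row is broken in the extracted text); use them if they are measured before any check-up content. Present no t-test or Cohen's d by use as an effect, and state that residual confounding remains.

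The TPB items matter because adjusting for arm and baseline outcome alone left up to 33% false positives in the table above, and 48% for visit rate. In the settings tried (r = 0.3 in all models, r = 0.5 in model A), adjusting for the motivation variable itself brought rejection back to about 5%. That is an ideal case, since real items carry measurement error.

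If the pathway from check-up through use to outcome is what is meant, name a causal mediation method and state its assumptions.

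The cost is rewording one exploratory sentence, with no new data apparently needed and no change in sample size. The downsides are that the use result becomes explicitly observational, the TPB items add covariates in a sample of 40, and the estimate by arm remains imprecise at 20 per arm.
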